8.4.1 Electrocardiograms

The Fridericia QT correction formula (QTcF) must be used for clinical decisions to assess eligibility. The investigator must calculate QTcF if it is not auto-calculated by the ECG machine.

Single 12 lead ECGs are collected.

ECGs will be locally collected and evaluated. Interpretation of the tracing must be made by a qualified physician and documented on the appropriate CRF. Each ECG tracing should be labeled with the study number, participant initials (where regulations permit), participant number, date, and kept in the source documents at the study site. Clinically significant abnormalities present at screening should be reported on the appropriate CRF. Clinically significant findings must be discussed with Novartis prior to enrolling the participant in the study. New or worsened clinically significant findings occurring after informed consent must be recorded as adverse events.

The original ECGs on non-heat-sensitive paper, appropriately signed, must be archived at the study site.

Additional, unscheduled, safety ECGs may be repeated at the discretion of the investigator at any time during the study as clinically indicated. For any ECGs with participant safety concerns, two additional ECGs must be performed to confirm the safety finding. ECG safety monitoring, or a review process, should be in place for clinically significant ECG findings during the study.

Clinically significant abnormalities must be recorded on the CRF as either medical history/current medical conditions or adverse events as appropriate.

8.4.2 Clinical safety laboratory tests

Clinically significant abnormalities must be recorded as either medical history/current medical conditions or adverse events as appropriate.

In all cases, the Investigator must document in the source documents the clinical considerations (i.e., result was/was not clinically significant and/or medically relevant) in allowing or disallowing the participant to continue in the study.

A central laboratory will be used for analysis of all safety specimens collected. Details on the collection, shipment of samples and reporting of results by the central laboratory are provided to investigators in the central laboratory manual.

If participants cannot visit the site for safety lab assessments conducted through central labs, local lab collection may be used during a Public Health Emergency as declared by local or regional authorities (i.e. pandemic, epidemic or natural disaster that limits or prevents on-site study visits).

Urinalysis

A midstream urine sample (approx. 30 mL) will be obtained, in order to avoid contamination with epithelial cells and sediments, and allow proper assessments.

Special clinical laboratory evaluations

In addition to hematology and clinical chemistry safety laboratory and urinalysis, thyroid-specific assays, endocrine function tests, and coagulation assays will be obtained as per the [Table 8-2](#) below.

All abnormal lab results must be evaluated for criteria defining an adverse event and reported as such if the criteria are met. For those lab adverse events, repeated evaluations are required to allow the determination of the outcome of the event where possible.

Clinically notable laboratory findings are defined in Appendix 3 ([Section 10.3](#)).

Table 8-2 Clinical Laboratory Evaluations

Test Category	Test Name
Hematology	Hematocrit, Hemoglobin, Ery. Mean Corpuscular Hemoglobin, Ery. Mean Corpuscular HGB Concentration, Ery. Mean Corpuscular Volume, Platelets, Erythrocytes, Leukocytes, Erythrocyte Cell Morphology (only to be assessed in case of abnormalities in the full blood count), Differential (Basophils, Eosinophils, Lymphocytes, Monocytes, Neutrophils, Bands)
Chemistry	Albumin, Alkaline phosphatase, ALT, AST, Gamma-glutamyl-transferase (GGT), Lactate dehydrogenase (LDH), Bicarbonate, Calcium, Magnesium, Phosphate, Chloride, Sodium, Potassium, Creatinine, Creatine kinase, Direct Bilirubin, Indirect Bilirubin, Total Bilirubin, Total Cholesterol, LDL Cholesterol, HDL Cholesterol, Total Protein, Triglycerides, Urea Nitrogen or Urea, Uric Acid, Amylase, Lipase, Glucose (non-fasting)
Urinalysis	Microscopic Panel (Erythrocytes, Leukocytes, Casts, Crystals, Bacteria, Epithelial cells) Macroscopic Panel (Dipstick) (Color, Bilirubin, Occult Blood, Macroscopic Blood, Glucose, Ketones, Leukocytes esterase, Nitrite, pH, Protein, Specific Gravity, Urobilinogen)
Coagulation	Prothrombin Time (PT), International Normalized Ratio (INR), activated Partial Thromboplastin Clotting Time (aPTT)
Liver Event Testing and Liver Follow-Up Testing	Albumin, ALP, ALT, AST, CK, GGT, GLDH, INR, PT, and Total Bilirubin (TBIL). Test for hemolysis (haptoglobin, reticulocytes, unconjugated [indirect] bilirubin).

CCI

Test Category	Test Name
	These tests are in addition to routine testing, to be performed only in follow-up to safety events when indicated in Section 10.5 Liver safety monitoring.
Renal follow-up	Tests that may be done in addition to routine testing (i.e. serum chemistry & urinalysis), to be performed in case of follow-up to renal safety events when indicated in Section 10.6 , Renal safety monitoring: Urine protein, albumin and creatinine (for urine protein; creatinine ratio (UPCR) and urine albumin; creatinine ratio (UACR)), repeat Serum Creatinine. Repeat standard chemistry testing and standard urinalysis (Microscopic Panel (Casts, Crystals, Bacteria, Epithelial cells, Erythrocytes, Leukocytes) and Macroscopic panel (Dipstick) (Color, Bilirubin, Glucose, Ketones, Leukocytes esterase, Macroscopic Blood, Nitrite Occult Blood, pH, Protein, Specific Gravity, Urobilinogen)), urine sediment & microscopy
Additional tests	NT-proBNP (considered a pharmacodynamic biomarker)
Pregnancy Test	Serum pregnancy test refer to 'Pregnancy testing' in Section 8.4.3

8.4.3 Pregnancy testing

A condom is required for all sexually active male participants to prevent them from fathering a child AND to prevent delivery of study treatment via seminal fluid to their partner. In addition, male participants should not donate sperm while taking drug and for 24 hours after stopping study medication.

All pre-menopausal women who are not surgically sterile will have pregnancy testing. Additional pregnancy testing might be performed if requested by local requirements.

As per [Section 4.5](#), during a public health emergency as declared by local or regional authorities (i.e. pandemic, epidemic or natural disaster, that limits or prevents on-site study visits), if participants cannot visit the site to have serum pregnancy tests, urine pregnancy test kits may be used. Relevant participants can perform the urine pregnancy test at home and report the result to the site. It is important that participants are instructed to perform the urine pregnancy test first and only if the test result is negative proceed with the administration of the study treatment. A communication process should be established with the participant so that the site is informed and can verify the pregnancy test results (e.g. following country specific measures).

Assessments of fertility

A woman is considered of childbearing potential from menarche and until becoming postmenopausal unless permanently sterile. Permanent sterilization methods include hysterectomy, bilateral salpingectomy and bilateral oophorectomy. Medical documentation of oophorectomy, hysterectomy, or tubal ligation must be retained as source documents.

A postmenopausal state is defined as no menses for 12 months without an alternative medical cause and an appropriate clinical profile.

In absence of the medical documentation confirming permanent sterilization, or if the postmenopausal status is not clear, the investigator should use his medical judgment to appropriately evaluate the fertility state of the woman and document it in the source document.

8.4.4 Appropriateness of safety measurements

CCI

Cardiac function and status are monitored by efficacy assessments including RHC, echocardiography, and 6MWT which are detailed under the efficacy measures in the study.

Further safety assessments (hematology, serum chemistry, coagulation, ECGs, vital signs, physical exams) are standard for investigations monitoring general safety in Phase 2 clinical trials.

8.5 Additional assessments

8.5.1 Clinical Outcome Assessments (COAs)

Patient Reported Outcomes

The participant must be given the PRO measures to be completed at the scheduled visit before any clinical assessments are conducted. Participant's refusal to complete all or any part of a PRO measure should be documented in the study data capture system and should not be captured as a protocol deviation.

Participant questionnaires should be completed in the language most familiar to the participant.

The participant should be given sufficient space and time to complete the PRO measures.

The site personnel should check PRO measures for completeness and ask the participant to complete any missing responses. The responses either captured on paper, and subsequently entered manually into the eCRF, or stored electronically in the database will be considered the source file.

Completed measures must be reviewed and assessed by the Investigator for responses which may indicate potential AEs or SAEs before any clinical study examinations. This assessment should be documented in study source records. If AEs or SAEs are confirmed, Investigators should not encourage the participant to change responses reported in the completed questionnaires. Investigators must follow reporting instructions outlined in [Section 8.6](#) of the study protocol.

The two patient reported outcomes utilized in this study are emPHasis-10 and PAH-SYMPACT. EmPHasis-10 is a total of 10 questions on an ordinal scale to determine the impact pulmonary arterial hypertension has on aspects of health-related quality of life. PAH-SYMPACT is a validated PAH-specific scale that monitors participant symptoms and clinical experience that is sensitive to improvement.

The Borg scale being used in conjunction with the 6MWT is also a PRO, but is handled separately, as described in [Section 8.3.3](#).

8.6 Adverse events (AEs), serious adverse events (SAEs), and other safety reporting

8.6.1 Adverse events

An adverse event (AE) is any untoward medical occurrence (e.g. any unfavorable and unintended sign [including abnormal laboratory findings], symptom or disease) in a clinical investigation participant after providing written informed consent for participation in the study. Therefore, an AE may or may not be temporally or causally associated with the use of a medicinal (investigational) product.

The Investigator has the responsibility for managing the safety of individual participant and identifying adverse events. Novartis qualified medical personnel will be readily available to advise on trial-related medical questions or problems.

The occurrence of adverse events must be sought by non-directive questioning of the participant at each visit during the study. Adverse events also may be detected when they are volunteered by the participant during or between visits or through physical examination findings, laboratory test findings, or other assessments.

Adverse events must be recorded under the signs, symptoms, or diagnosis associated with them, accompanied by the following information (as far as possible) (if the event is serious refer to [Section 8.6.2](#)):

1. The severity grade
 - mild: usually transient in nature and generally not interfering with normal activities
 - moderate: sufficiently discomforting to interfere with normal activities
 - severe: prevents normal activities

2. Its relationship to the study treatment. If the event is due to lack of efficacy or progression of underlying illness (i.e. progression of the study indication) the assessment of causality will usually be 'Not suspected.' The rationale for this guidance is that the symptoms of a lack of efficacy or progression of underlying illness are not caused by the trial drug, they happen in spite of its administration and/or both lack of efficacy and progression of underlying disease can only be evaluated meaningfully by an analysis of cohorts, not on a single participant
3. Its duration (start and end dates or ongoing) and the outcome must be reported
4. Whether it constitutes a SAE (see [Section 8.6.2](#) for definition of SAE) and which seriousness criteria have been met
5. Action taken regarding with study treatment.

All adverse events must be treated appropriately. Treatment may include one or more of the following:

- Dose not changed
- Dose Reduced/increased
- Drug interrupted/permanently discontinued

6. Its outcome

Conditions that were already present at the time of informed consent should be recorded in medical history of the participant.

Adverse events (including lab abnormalities that constitute AEs) should be described using a diagnosis whenever possible, rather than individual underlying signs and symptoms.

Adverse event monitoring should be continued for at least 30 days following the last dose of study treatment.

Once an adverse event is detected, it must be followed until its resolution or until it is judged to be not recovered/not resolved (e.g. continuing at the end of the study), and assessment must be made at each visit (or more frequently, if necessary) of any changes in severity, the suspected relationship to the interventions required to treat it, and the outcome.

Information about adverse drug reactions for the investigational drug can be found in the Investigator's Brochure (IB).

Abnormal laboratory values or test results constitute adverse events only if they fulfill at least one of the following criteria:

- they induce clinical signs or symptoms
- they are considered clinically significant
- they require therapy

Clinically significant abnormal laboratory values or test results must be identified through a review of values outside of normal ranges/clinically notable ranges, significant changes from baseline or the previous visit, or values which are considered to be non-typical in a participant with the underlying disease.

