9.3.1 Definition of primary endpoint(s)

Adverse events (AEs)

Study emergent AEs in the extension study will be summarized and listed. Also, all study emergent AEs in both the parent study and extension study will be summarized.

Consistent with the parent study CLTP001A12201 definitions, AEs starting after the first dose of study medication or events present prior to start of treatment but increased in severity based on preferred term will be classified as a treatment emergent AE. The following treatment emergent adverse events summaries will be produced:

- by primary system organ class and preferred term
- by primary system organ class, preferred term and maximum severity
- by Standardized MedDRA Query (SMQ) and preferred term.

The number and percentage of participants with adverse events will be summarized.

Vital signs

Vital signs data will be summarized by visit/time.

Electrocardiogram (ECG)

All ECG data, including PR, QRS, QT, QTcF and RR, will be listed by participant and visit/time, and abnormalities will be flagged. Summary statistics will be provided by visit/time. Categorical Analysis of QTcF (Fridericia's formula) interval data based on the number of participants meeting or exceeding predefined limits in terms of absolute QT or QTc intervals or changes from baseline will be presented. The number and percentage of participants with clinical notable QTcF will be summarized.

Laboratory data

All laboratory data will be listed by participant and visit/time, and abnormalities will be flagged if normal ranges are available. Summary statistics will be provided for each lab parameter at each visit.

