2.3.2 Demographics and other baseline characteristics

Demographics and other extension study baseline data that will be assessed will be summarized descriptively utilizing the safety set. Categorical data will be presented as frequencies and percentages. For continuous data, mean, standard deviation, median, minimum, and maximum will be presented. For selected parameters, 25th and 75th percentiles will also be presented.

Participant demographics will include age, gender, race, ethnicity & BMI.

Relevant medical history and current medical conditions at the baseline will be listed by participant.

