2.5.1 Primary endpoint(s)

Safety assessment will include AEs, SAEs, vital signs, ECGs, and safety laboratory measurements.

Adverse events (AEs)

All Adverse events in the extension study will be summarized and listed. Also, all study emergent AEs in both the parent study and extension study will be summarized.

Consistent with the parent study CLTP001A12201 definitions, AEs starting after the first dose of study medication or events present prior to start of treatment but increased in severity based on preferred term will be classified as a treatment emergent AE. The definition of the on treatment period is defined in [Section 2.1.1](#). The following treatment emergent adverse events summaries will be produced:

- by primary system organ class and preferred term
- by primary system organ class, preferred term and maximum severity
- by Standardized MedDRA Query (SMQ) and preferred term.

The number and percentage of participants with adverse events will be summarized.

Separate summaries will be provided for study medication related adverse events, serious adverse events, other significant adverse events leading to discontinuation. In case of sparse events in any of these categories occur, only a listing will be provided if deemed adequate.

The number and percentage of deaths, including on-treatment and post-treatment deaths, will be summarized and listed.

Adverse events of special interest/grouping of AEs is not defined in this study.

Vital signs

Vital signs will include the collection of otic or oral body temperature (recorded in °C), blood pressure (BP) and pulse measurements.

All vital signs data will be listed by participant, and visit/time and if ranges are available, abnormalities will be flagged. Summary statistics (including N, mean, SD, minimum, median, maximum) of vital signs and changes from baseline will be provided by visit/time. Graphical presentations (e.g., boxplots) of vital signs will be provided by visit/time.

Electrocardiogram (ECG)

All ECG data, including PR, QRS, QT, QTcF and RR, will be listed by participant and visit/time, and abnormalities will be flagged. Summary statistics and graphical presentations (e.g. boxplots) will be provided by visit/time.

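### Parent-study AEs still ongoing at rollover are recorded as medical history, so their persistence, outcome and any resulting withdrawal have no defined record in the extension

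*Protocol*

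**What the plan says.** **Recording.** Protocol 8.6.1 limits an AE to an occurrence "after providing written informed consent for participation in the study". The same section then directs: "Conditions that were already present at the time of informed consent should be recorded in medical history of the participant". Table 8-1 in Protocol 8.4 applies the same split to physical examination findings: those present before consent go on the medical history form, and later ones that meet the definition are AEs. None of these places mentions AEs carried over from the parent study.

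**Follow-up.** Protocol 8.6.1 also states: "Once an adverse event is detected, it must be followed until its resolution or until it is judged to be not recovered/not resolved". It does not say whether this covers an AE opened in the parent study.

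**Analysis.** Protocol 9.3.1 and SAP 2.5.1 plan two outputs. One covers the extension alone; the SAP words it as "All Adverse events in the extension study will be summarized and listed". The other is combined: "Also, all study emergent AEs in both the parent study and extension study will be summarized". Treatment-emergent events are "AEs starting after the first dose of study medication or events present prior to start of treatment but increased in severity based on preferred term". SAP 2.5.1 adds summaries of drug-related AEs, serious AEs and AEs leading to discontinuation.

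**Medical history.** SAP 2.3.2 plans a listing only: "Relevant medical history and current medical conditions at the baseline will be listed by participant".

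**The concern.** Sending pre-existing conditions to medical history suits a trial in which consent comes before any exposure. Here consent is taken around the parent end-of-treatment visit at Week 25 (Protocol 4.1). For someone who received LTP001 in the parent study, a condition present at that moment may have begun on the drug. The rule makes it part of the baseline.

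The primary objective is long-term safety. For a tolerated, non-serious event that does not go away, the useful long-term questions are how long it lasts, whether it resolves on continued treatment, and whether it eventually causes withdrawal. Protocol 8.6.1 asks for severity, relationship, duration, outcome and action taken for AEs. It asks for none of these for medical history.

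**Working it through.** The plan gives no AE rate, persistence rate or sample size calculation, so there is no figure to reproduce. The check traces one AE through the rules: onset on parent-study treatment, still present when extension consent is signed.

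| Course after rollover | AE record required in the extension | Extension-only AE tables | Combined parent and extension summary |
|---|---|---|---|
| Unchanged | None; medical history | Not counted | Occurrence counted; persistence not shown |
| Resolves | None; medical history | Not counted | Occurrence counted; resolution not shown |
| Worsens | Yes | Counted as treatment emergent | Counted |
| Unchanged, but LTP001 is stopped because of it | None; medical history | May be missing from the leading-to-discontinuation summary | Occurrence counted; link to stopping not shown |

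The third row rests on the clause covering "events present prior to start of treatment but increased in severity based on preferred term".

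Other provisions that might supply the missing information were then checked.

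1. **Parent follow-up visit.** SAP 2.1.1 says the parent end-of-study visit is skipped for participants who enter the extension, so that visit does not capture the later course.
2. **Update at entry.** Protocol 8.2 asks about changed medical conditions only when applicable, giving a significant enrollment delay as the case. Direct rollover is allowed and is not covered.
3. **Record linkage.** Protocol 5.4.1 assigns the next sequential participant number at consent. Nothing describes linking AE records across the two studies.
4. **Disposition.** SAP 2.3.1 tabulates discontinuation from the study by primary reason. Protocol 7.1 and 7.2 treat stopping study treatment and leaving the study as different things, and the disposition table does not name the event.
5. **Serious events.** Protocol 8.6.3 requires follow-up information on each serious AE, so the gap mainly concerns non-serious events.

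**The anchor date is also unclear.** Treatment emergence runs from the first dose of study medication. SAP 2.1.1 defines Day 1 as the first actual administration of LTP001, but counts study day from the first dose of LTP001 or placebo. For former LTP001 participants both can point to the parent study. On that reading the same event is treatment emergent for analysis and medical history for recording.

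**Scale.** With about 40 participants planned (Protocol 1.1 and 5), one participant is 1/40 = 2.5 percentage points of a descriptive table. This shows what one uncounted case is worth; it does not estimate how many there are.

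**The case against.** The strongest reply is that the plan does not ignore these events. The combined summary counts each one's occurrence, and worsening enters the extension tables. Vital signs, ECGs and laboratory values are themselves primary endpoints, and SAP 2.1 reports changes from the parent baseline as well as the extension baseline, so a persistent measured abnormality stays visible however it is coded. Eligibility also limits what is at stake: entry requires that parent discontinuation criteria were not met, and permanent discontinuation for toxicity excludes a participant (Protocol 5.1 and 5.2). All of this stands. It means a reader should not infer that the extension safety results leave these events out altogether.

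A reader might also infer that the tables are biased towards fewer events in former LTP001 participants. The documents do not support that. The recording rule applies to every rollover participant, including those who had placebo, and SAP 2.5.1 does not split AE summaries by parent treatment. An extension-only table of new-onset events is a normal incidence measure. Mixing in parent-onset events would blur incidence with prevalence and could count an event twice. That is a good reason for a separate row.

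Finally, the parent protocol is not available and may keep such AEs open after rollover. That would reduce the loss. It would not change what this protocol tells sites to record, and neither document says how such parent data would reach the extension tables.

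**Conclusion.** The point holds in a limited form. Protocol 8.6.1 states a rule without the exception that a rollover study needs. For an AE that began in the parent study and is unchanged at extension consent, no provision in either document defines where its later duration, outcome or action taken is recorded, and the leading-to-discontinuation summary may have no AE to count if LTP001 is stopped because of it. Occurrence and worsening are covered; persistence, outcome and attribution of discontinuation may not be.

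The number of participants affected cannot be calculated: neither the parent allocation nor any AE persistence rate is given. The conclusion assumes that sites apply the recording rule as written and that no unseen form-completion guideline or parent-study rule overrides it. It is worth correcting because the missing information bears directly on the primary objective.

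**What to change.** **Protocol 8.6.1 (and Table 8-1 to match).** State that for all rollover participants, whatever their blinded parent treatment, each parent-study AE ongoing at extension consent stays open as an AE. It is either carried forward with its original onset date or linked to the parent record, with severity, outcome and action taken updated during the extension. It is not entered as medical history.

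**SAP 2.5.1.**
- Show these events in a separate row, labelled for example 'onset in parent study, ongoing at extension Day 1', by parent treatment and apart from new-onset extension AEs.
- Count each once in the combined summary and report its outcome.
- Include an event in the leading-to-discontinuation summary if LTP001 is stopped because of it.
- State for each table which first dose anchors treatment emergent.

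**Cost.** A short protocol addition and an SAP paragraph, plus the work of linking and de-duplicating parent and extension AE records. Sites need no unblinding, because the split by parent treatment is made at analysis. No dose, visit or discontinuation rule changes.
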